### Safety endpoints:

[figure not shown]
- 1. Increase in serum creatinine by 26.5  $\mu$ mol/L (0.3 mg/dL) or more and/or a  $\geq$ 25% increase in serum creatinine OR a  $\geq$ 20% drop in GFR) at discharge
- 2. Access-related complications (bleeding, infection)

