### Treatment:

### Ultrafiltration group:

Patients in the intervention group will be treated with veno-venous ultrafiltration (UF) complementary to low-dose diuretic therapy according to the low-dose IV diuretic treatment algorithm and other medical therapy as judged indicated by the investigator. Patients will receive 1-7 UF sessions (6-10h/session, number of sessions depending on clinical assessment according to algorithm) during a maximum time period of 10 days.

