### Target variables:

Primary endpoint:

Composite endpoint of cardiovascular mortality in 90 days after randomization and heart failure events in 90 days after discharge. HF events are defined as HF rehospitalization or an urgent HF visit.

Secondary endpoints:

- 1. Heart failure rehospitalization analyzed as a recurrent event in 90 days after discharge
- 2. Time until first HF rehospitalization in 90 days after discharge
- 3. Time until first urgent HF visit in 90 days after discharge
- Quality of life (Patient Global Assessment at baseline, discharge, FU30, FU90; Short Kansas City Cardiomyopathy Questionnaire and EQ-5D-5L at discharge, FU30, FU90)
- 5. Days alive and out of hospital up to 90 days after discharge
- 6. Cardiovascular mortality in 90 days after randomization
- 7. Resolution of congestion defined as at least two of the final eligibility criteria present at randomization have resolved (this does not include chest x-ray criterion, i.e. if x-ray criterion was one out of two final eligibility criteria, only resolution of the other criterion necessary), thus:
  - Jugular venous pressure of <8cm H2O
  - No orthopnea
  - Trace or no peripheral edema
  - Respiratory rate no longer  $\geq$  20/minute
- 8. In-hospital worsening heart failure until discharge
- 9. Weight loss at 96h after randomization and at discharge

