### Exploratory variables:

- 1. Length of stay during initial hospitalization
- 2. Change in furosemide-equivalent dose from preadmission to discharge (in mg/day)
- 3. All-cause mortality rates up to 90 days after randomization

, ,	
Data Base Lock	Q 3 2021
Statistical Analysis and Report	Q 4 2021

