### **1.3.** SAFETY ANALYSES

Standard procedures for reporting of adverse events will be used. Adverse events will be summarized as frequencies and percentages by treatment group.

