### Handling of missing data

We will perform multiple imputation for subjects with missing data on the primary and secondary outcomes at 90 days, if applicable (details will be specified in the SAP).

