### Safety-population (SP)

Includes all subjects who were randomized.

Assignment of patients to analysis populations will be done during the data review meeting. Primary analysis will be based on the ITT population; an additional analysis on PP will be performed to assess validity of results. Safety analyses will be performed on the SP.

The primary endpoint measured at 90 days will be analyzed on an intention to treat basis. It is anticipated that there may be some "crossover" from the intervention group to the control group or from the control group to the intervention group. The number of crossovers will be documented to provide context for interpreting the primary results; however, treatment crossovers will be analyzed according to the intention to treat principle and thus will be included in the arm to which they were randomized.

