### **1.6.** SAMPLE SIZE JUSTIFICATION

Previously published results from clinical trials comparing intravenous loop diuretics to mechanical fluid removal by isolated veno-venous ultrafiltration have yielded conflicting results regarding heart failure-related rehospitalization. The present PURE-HF study is similar to the AVOID-HF (Costanzo et al., 2015) in terms of study design and targets. The primary objective of the AVOID-HF study was to determine whether UF prolonged the time to first HF event within 90 days of hospital discharge. Regarding sample size considerations, the AVOID-HF trial refers to different publications in order to provide an estimate of the combined HF event rate for the control group and the assumed reduction of the HF event rate in the UF group (Felker et al., 2011, O'Connor et al., 2011, Costanzo et al., 2007, Konstam et al., 2007, Hernandez et al., 2010, Ross et al., 2010).

Taking into account the assumptions and observations actually made in the prematurely terminated AVOID-HF study published by Costanzo et al. (Costanzo et al., 2016) we estimated that 864 patients (432 in each arm) should be sufficient to test whether there is a difference between the event proportions of the test and the control treatment. The proposed sample size calculations based on the two-sided Z test with unpooled variance and include the following assumptions: 1)  $\alpha$  of 0.05 ( $\alpha$ /2=0.025); 2) power (1- $\beta$ ) of 0.90; 3) an HF event rate for the loop diuretics group of 25% plus 2% cardiovascular death and 4) a reduction of the event proportion for the UF group of 37,5 % (this leads to an event proportion for the UF group of 16,88%). The estimated total sample size is displayed with additional patients included to account for 10% of subjects lost to follow-up and 13% treatment failures due to crossover during the treatment period

Event proportion			Sample size N		
control group	UF group	Reduction	Crude	Incl. 10% loss to FU	Incl. 10% loss to FU and 13% treatment failure
27.00%	16.88%	37.50%	694	764	864

- 1) Test for two proportions,
- 2) two-sided a of 0.05,
- 3) power of 0.90,
- 4) HF event rate of control group of 25% + 2% in-hospital death
- 5) an event proportion for the loop diuretics group (control group) of 27%,
- 6) an event proportion for the UF group (treatment group) of 16.88% (37.50% reduction),
- 7) including 10% loss to follow up and 13% crossover (i.e. treatment failure),

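### The renal safety endpoint is read only at discharge, so kidney injury that recovers before then, or is masked by in-hospital renal replacement, is not counted in it, and in-hospital deaths have no defined status

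*Combined protocol and SAP*

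**What the plan says.** In the Synopsis of the combined protocol and SAP, under Safety endpoints, the first endpoint is met by a creatinine rise of 0.3 mg/dL (26.5 µmol/L) or more and/or 25% or more, or by a GFR fall of at least 20%. The timing is given only by the closing words, "drop in GFR) at discharge". The value from which the change is measured is not stated. The second safety endpoint is access complications.

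Other parts of the plan that bear on this:

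- **Treatment period.** Ultrafiltration (UF) sessions may be given "during a maximum time period of 10 days" (Synopsis, Ultrafiltration group).
- **Timing of discharge.** "Length of stay during initial hospitalization" is itself an exploratory variable (Synopsis, Exploratory variables).
- **Contrast with weight.** Secondary endpoint 9 has a fixed reading as well as a discharge reading: "Weight loss at 96h after randomization and at discharge" (Synopsis, Target variables).
- **Safety population.** "Includes all subjects who were randomized" (section 1.5).
- **Other safety reporting.** "Adverse events will be summarized as frequencies and percentages by treatment group" (section 1.3).
- **Missing data.** Multiple imputation is planned for "missing data on the primary and secondary outcomes at 90 days" (section 1.4). Safety endpoints are not mentioned.
- **Expected deaths.** The assumptions list in section 1.6 includes "HF event rate of control group of 25% + 2% in-hospital death". The running text of the same section labels that 2% as cardiovascular death.

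**The concern.** Both arms undergo active fluid removal in hospital, so that is when treatment could affect the kidney. A single reading at discharge raises three problems.

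1. **Timing can depend on the arm.** Discharge follows randomisation and can be affected by treatment. If the arms are discharged at different times, creatinine is compared at different intervals after randomisation.
2. **Events that resolve are not counted.** Injury that recovers before discharge scores as no event. So may injury treated with renal replacement therapy, because the therapy itself lowers creatinine. Severe renal dysfunction needing such therapy is an exclusion at entry, but its start after randomisation is not part of the endpoint. If recovery or renal replacement differs by arm, the comparison is distorted and does not merely lose precision.
3. **In-hospital deaths have no discharge value.** They belong to the analysed population, but no rule says how they are classified.

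Access complications arise mainly in the device arm, so the renal endpoint is the main named safety endpoint on which the two strategies can be compared.

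**Working it through.** **Step 1: the plan's own figure.** No rate, power or sample size is stated for the renal endpoint. The only stated calculation is for the primary endpoint (section 1.6). With unpooled variance, n per arm = (z₀.₉₇₅ + z₀.₉₀)² × [p₁(1−p₁) + p₂(1−p₂)] / (p₁−p₂)². Putting in p₁ = 0.27 and p₂ = 0.1688:

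- 10.507 × (0.1971 + 0.1403) / 0.1012² = 346.2, so 347 per arm and 694 in total.
- 694 × 1.10 = 763.4, so 764.
- 764 × 1.13 = 863.3, so 864, or 432 per arm.

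The stated figures reproduce. Only the 432 per arm is used below.

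**Step 2: what is read when.** Weight is read at 96 h and at discharge. Worsening heart failure is followed through the whole index stay (secondary endpoint 8). Creatinine and GFR, for the safety endpoint, are read at discharge alone. UF may continue for up to 10 days, and length of stay is an outcome, so nothing in the text fixes the reading at the same time after randomisation in both arms.

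**Step 3: patients without a discharge value.** At the 2% of section 1.6, 432 × 0.02 = 8.6, or about 9 control patients. If the same rate held in both arms (an assumption), 864 × 0.02 = 17.3, or about 17 patients.

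**Step 4: how recovery before discharge acts.** Let an arm have injury proportion p during treatment, of which a fraction r recovers by discharge. The endpoint then sees p(1−r). Power is Φ(|d|/SE − 1.96) plus the negligible or small opposite tail, with SE = √{[a(1−a) + b(1−b)]/432}, where a and b are the proportions seen and d is their difference. All rates below are assumed; none is in the documents. H is the arm with more injury and L the other; the documents do not say which arm that would be.

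| Injury during treatment, H / L | Recovered by discharge, H / L | Seen at discharge, H / L | Difference (points) | Power, 432 per arm |
|---|---|---|---|---|
| 28% / 20% | 0% / 0% | 28% / 20% | 8.0 | 79% |
| 28% / 20% | 50% / 50% | 14% / 10% | 4.0 | 44% |
| 28% / 20% | 50% / 30% | 14% / 14% | 0.0 | no difference to detect |
| 28% / 20% | 70% / 50% | 8.4% / 10% | −1.6 | sign reversed |
| 28% / 20% | 30% / 50% | 19.6% / 10% | 9.6 | 98% |
| 25% / 15% | 0% / 0% | 25% / 15% | 10.0 | 96% |
| 25% / 15% | 40% / 40% | 15% / 9% | 6.0 | 78% |
| 25% / 15% | 60% / 40% | 10% / 9% | 1.0 | 8% |

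Equal recovery shrinks the difference. Unequal recovery can erase it, reverse it or, as in the fifth row, enlarge it.

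**Step 5: how much the deaths matter.** Take the 15% against 9% row, assume 2% deaths in both arms and count each death as an event. Then 0.02 + 0.98 × 0.15 = 16.7% and 0.02 + 0.98 × 0.09 = 10.8%, and the difference moves from 6.0 to 5.9 points. On these assumptions the missing rule for deaths is a gap in definition with little numerical effect. Timing matters more.

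**The case against.** **Discharge is a coherent target.** It measures the injury a patient leaves hospital with. This stands, and is a reason to keep the discharge reading. It does not justify having no reading during treatment.

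**Renal harm would not vanish from the trial.** Adverse events are tabulated by arm (section 1.3), the DMC reviews the database and event listings (section 1.7), and section 1.2 mentions changes in laboratory measurements. A reader might infer that a real renal harm could go wholly unseen; the documents do not support that. None of these sections, however, sets a renal threshold at a defined time, so they do not repair the endpoint.

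**Deaths are not excluded.** A reader might infer that in-hospital deaths drop out of the safety analysis. Section 1.5 keeps every randomised patient in the safety population, and deaths are also counted in the primary endpoint, secondary endpoint 6 and all-cause mortality. The plan is silent on their renal status; it does not remove them.

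**The magnitudes are assumed.** This is correct. The plan sets no powered renal hypothesis. The most striking rows need more recovery in the arm with more injury, and nothing in the text says that either arm stays longer. The 10 days is a maximum for UF, with no control duration visible to compare.

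**Alternative readings have faults too.** A worst in-hospital value gives patients who stay longer more chances to qualify, which brings back dependence on length of stay. A 96 h reading falls inside the possible UF period and misses later injury. Both points stand and shape the fix.

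**The text is partial.** Only the synopsis and statistics section are available, and a figure is missing beside this endpoint. A fuller laboratory schedule may exist, but collecting values would not change an endpoint defined at discharge.

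**Conclusion.** The point holds as a limit of this one endpoint. As written, it does not count kidney injury that arises during treatment and recovers before discharge, or that is masked by renal replacement therapy started in hospital. Its reading time may differ between arms. It states no reference value and gives in-hospital deaths no status.

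The size is unknown. The table shows the mechanism and its possible range, and is not an estimate of what this trial would find; a reader should not take the 8% power or the vanishing difference as a prediction. The one quantity that rests on the plan's own figure is about 9 of 432 control patients without a discharge value, and that depends on reading the 2% as in-hospital death. No stated number in the plan is wrong because of this point, and the sample size and primary analysis are unaffected. It is a cheap improvement that should be made.

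**What to change.** Change the endpoint definition as follows.

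1. Apply the same creatinine/GFR criterion at 96 h after randomisation, the time already used for weight, and keep discharge as a second reading.
2. State the reference: the pre-randomisation value. Because patients have already received IV loop diuretics before screening, say which pre-randomisation sample is meant.
3. Count the start of renal replacement therapy in hospital as meeting the endpoint.
4. Report in-hospital deaths without a discharge value as a separate category and, in a sensitivity analysis, as events. State the matching rule for patients who die or are discharged before 96 h.
5. If a worst value is also reported, restrict it to a fixed window after randomisation that is the same in both arms, for example through day 10, the maximum UF period.

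**Cost.** Endpoint wording, a few lines in the SAP, and one creatinine value at 96 h if it is not already recorded; the laboratory schedule is not visible, so this cannot be confirmed. A 96 h reading alone misses later injury and may count transient rises, which is why discharge is kept beside it. Counting deaths as events mixes mortality into a renal measure, so that belongs in the sensitivity analysis only.

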### Exploratory variables:

- 1. Length of stay during initial hospitalization
- 2. Change in furosemide-equivalent dose from preadmission to discharge (in mg/day)
- 3. All-cause mortality rates up to 90 days after randomization

, ,	
Data Base Lock	Q 3 2021
Statistical Analysis and Report	Q 4 2021

### Intervention scheme and trial flow:

Of note, patients must be randomized within 24 hours after admission to designated hospital floor.

### 1. STATISTICS

### **1.1. PRIMARY ANALYSIS**

The primary endpoint of the trial is the composite of cardiovascular mortality in 90 days after randomization or a heart failure event in the 90 days after discharge.

The primary analysis of the effectiveness of the UF treatment will be conducted in the ITT population (see section 1.5). The occurrence of cardiovascular deaths or heart failure event after discharge from hospital will be summarized using event proportions, i.e. number of patients with an event divided by the number of patients randomized to the respective treatment group.

The null hypothesis of no difference in event proportions between the randomized groups will be tested in a two sided test using logistic regression analysis adjusting for stratification variables (other than study site). Odds ratios including 95% confidence intervals (CI) will be presented as well as p-values (Wald methodology). In addition, descriptive analyses of the components of the primary outcome will be reported in the form of Kaplan-Meier (KM) curves for the time-to-event for each of cardiovascular mortality in 90 days after randomization and heart failure event within 90 days after discharge (Kaplan and Meier, 1958). Follow-up times will be censored at date of death, loss to follow-up or at the 90 day cut-off period.

Hazard ratios comparing the two treatment groups under study will be determined within the Cox proportional hazard model and provided along with the 95% HR confidence limits (Wald-CI).

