### Study-specific:

- Acute coronary syndrome requiring intervention during index hospitalization
- Severe renal dysfunction requiring renal replacement therapy
- Systolic blood pressure <90 mmHg at the time of randomization
- Pulmonary hypertension not secondary to left heart disease
- Pulmonary disease thought to be primarily responsible for symptoms
- Contraindication to systemic anticoagulation
- Severe concomitant disease expected to prolong hospitalization or to cause death in ≤90 days
- Sepsis
- Severe uncorrected valvular stenosis at the time of randomization
- Active myocarditis
- Hypertrophic obstructive cardiomyopathy
- Constrictive pericarditis or restrictive cardiomyopathy
- Liver cirrhosis due to primary liver disease
- Known infection with human immunodeficiency virus (HIV) or active hepatitis C
- Previous solid organ transplant
- Presence or requirement for mechanical respiratory support
- Presence or requirement of a mechanical circulatory support device
- Need for IV positive inotropic agents at the time of randomization

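### The primary logistic model names no covariate beyond the stratification variables; adding baseline values the plan already needs would be a modest efficiency gain, not the correction of an error

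*Combined protocol and SAP*

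**What the plan says.** Section 1.1 of the combined protocol and SAP tests equality of event proportions by "logistic regression analysis adjusting for stratification variables (other than study site"). On the result it says: "Odds ratios including 95% confidence intervals (CI) will be presented as well as p-values (Wald methodology"). It names no further covariate, and the available text does not say what the stratification variables are.

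Other parts of the plan need baseline information:
- **Creatinine or GFR.** The first safety endpoint begins "Increase in serum creatinine by 26.5" µmol/L and is a change assessed at discharge, so it needs a starting value.
- **Preadmission diuretic dose.** The second exploratory variable is "Change in furosemide-equivalent dose from preadmission to discharge".
- **Systolic pressure.** A study-specific exclusion criterion is "Systolic blood pressure <90 mmHg at the time of randomization", so the pressure has to be checked then.
- **Age.** It is an eligibility item, and section 1.2 gives it as an example of a subgroup variable.

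Section 1.2 plans adjustment for baseline level only in the linear regression of continuous endpoints. It leaves further methodological detail to the SAP.

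**The concern.** For a binary outcome, adjusting for pre-specified baseline covariates that predict the outcome increases the power of the treatment test and reduces the influence of chance imbalance. Here the candidate values should need little or no new data collection. The plan already accepts baseline adjustment for continuous secondary endpoints but does not extend it to the one test that decides the trial. If the covariates are not fixed in advance, an adjusted analysis prompted by an imbalance seen in the data would be post hoc.

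**Working it through.** **Inputs from section 1.6.** The plan gives "two-sided a of 0.05", power 0.90, "an event proportion for the loop diuretics group (control group) of 27"%, and "an event proportion for the UF group (treatment group) of 16.88% (37.50% reduction"). The total is 864, 1:1, with allowance for 10% loss to follow-up and 13% crossover.

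**Step 1: reproduce the plan's sample size.** For the two-sided Z test with unpooled variance:

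n per arm = (1.960 + 1.2816)² × [0.27 × 0.73 + 0.1688 × 0.8312] / (0.27 − 0.1688)² = 10.507 × 0.33741 / 0.010241 = 346.2.

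This rounds up to 347 per arm, 694 in total. Then 694 × 1.10 = 763.4, rounded up to 764, and 764 × 1.13 = 863.3, rounded up to 864. The stated 694 / 764 / 864 are reproduced. They rest on an unadjusted comparison and take no credit for covariates.

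**Step 2: power of the logistic Wald test without covariates.** With p₂ = 0.16875, the odds ratio is (0.16875/0.83125) / (0.27/0.73) = 0.549, log −0.600. At 347 per arm, SE = √[(1/0.1971 + 1/0.1403)/347] = 0.1875. Power = Φ(0.600/0.1875 − 1.960) = Φ(1.24) = 89.2%. This is slightly below 90% because the test is on the log-odds scale.

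**Step 3: add one baseline risk score.** The model is logit P(event) = a + c·t + b·x, where t is the arm and x is standard normal. The slope b is set so that x has the assumed AUC in the control arm. The constants a and c are solved so that the marginal event proportions stay at 27% and 16.875%. Power is Φ(|c|/SE − 1.960), with SE from the expected Fisher information for (1, t, x). **The AUC is an assumption; the documents give none.**

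| Assumed AUC | Conditional OR | Power, N = 694 | Gain (points) | N for the unadjusted power |
|---|---|---|---|---|
| no score | 0.549 | 89.2% | – | 694 |
| 0.55 | 0.547 | 89.4% | 0.2 | 690 (0.5% fewer) |
| 0.60 | 0.542 | 89.9% | 0.6 | 679 (2.1%) |
| 0.65 | 0.532 | 90.6% | 1.4 | 661 (4.8%) |
| 0.70 | 0.517 | 91.8% | 2.5 | 633 (8.8%) |
| 0.75 | 0.495 | 93.2% | 4.0 | 596 (14.1%) |

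How the gain arises at AUC 0.65: |c| grows from 0.600 to 0.631, about 5%. The SE implied by 90.6% power is 0.631/(1.32 + 1.96) = 0.192, about 3% larger than 0.1875. The ratio therefore rises from 3.20 to 3.28.

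Simulations with 4,000 runs per row, comparing both tests on the same data, gave gains of 0.25, 0.25, 0.7, 2.5 and 3.65 points from AUC 0.55 to 0.75. That is the same direction and order of size.

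**Step 4: allow for loss and crossover.** Assume 864 × 0.90 = 778 analysed, crossover from UF to control only, and the control event rate after crossover. The UF proportion becomes 0.87 × 0.16875 + 0.13 × 0.27 = 0.1819. Unadjusted power is 83.2%. With the score it is 83.4, 84.0, 85.0, 86.5 and 88.5% for the same AUC values, a gain of 0.2 to 5.3 points.

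**Step 5: type I error.** In 6,000 simulated null trials at N = 778 and AUC 0.65, the rejection rate was 4.8% adjusted and 4.9% unadjusted.

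**Step 6: the strata.** The table compares a score with no covariates, whereas the actual choice is between the strata alone and the strata plus extra covariates. If the strata alone already gave AUC 0.60 and the extra covariates raised it to 0.65, the gain at N = 694 would be about 90.64 − 89.85 = 0.8 points, not 1.4.

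**The case against.** The strongest reply is that nothing is wrong. Logistic regression adjusted for the stratification variables is a valid, common, pre-specified choice, and the sample size was not built on anything more. That stands.

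The benefit is also uncertain, for four reasons that stand as well:
- The stratification variables are not named in the available text, so renal function, for example, may already be in the model. Material was removed from the documents before review, so this silence cannot be counted against the plan.
- The documents nowhere call these variables prognostic for the 90-day composite.
- The systolic pressure criterion is a threshold check. It does not show that a number is stored as analysis data. Completeness of the other values is not stated either.
- The calculation uses one correctly specified score. Four separate terms with assumed forms and some imputed values would do somewhat less well.

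A reader might infer that power is being left unused for free. The documents do not support that. The gain depends on an unknown prognostic strength, and there is a price in interpretation: section 1.1 frames the null hypothesis in event proportions, while each added covariate moves the conditional odds ratio away from the marginal one (0.549 to 0.532 at AUC 0.65).

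The deferral of detail to the SAP in section 1.2 answers the point only in part. It sits with the secondary analyses and names no covariates for the primary model.

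**Conclusion.** The point holds as a modest, cheap efficiency improvement. No covariate beyond the stratification variables is named for the primary test. Creatinine or GFR, preadmission diuretic dose and age must be available, and systolic pressure probably is.

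If these values are prognostic, the gain at N = 694 is about 0.2 to 4 points of power for an AUC of 0.55 to 0.75. It is under 2 points up to AUC 0.65, and smaller again if the strata are prognostic. Type I error is unaffected. The result assumes the planned event proportions and a single correctly specified score.

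It would be wrong to conclude that the primary analysis is invalid, that the sample size is miscalculated on this account, or that the plan is shown to omit renal function from the model. The sample size reproduces without any covariate, and the content of the strata is unknown.

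**What to change.** Before unblinding, amend section 1.1 as follows:

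1. Name the stratification variables that enter the primary model.
2. Add those of the following that are not already strata: age, baseline GFR (or log creatinine), log preadmission furosemide-equivalent dose, and systolic pressure at randomization if it is recorded as a number. Enter them as linear terms, with simple imputation of missing baseline values.
3. Beside the conditional odds ratio, report a standardised (marginal) risk difference with 95% CI from the same model, so that the estimate addresses event proportions, as the null hypothesis does.
4. Keep the strata-only model as a sensitivity analysis.

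The cost is a few lines of wording and no extra patients. The downsides are an odds ratio conditional on more covariates and a gain that may prove small; a weakly prognostic score (AUC 0.55) still gave about 0.2 points.
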